#### Attachments

#### Subject Recruitment Methods & Advertising

Describe how the study team will identify and recruit subjects. Please consider the following items and provide additional information as needed so that the IRB can follow each step of the recruitment process.

- How will the study team identify potential participants?
- Who will first contact the potential subjects, and how?
- Will you use advertisements? If so, how will you distribute those?
- How and where will the research team meet with potential participants?
- If applicable, describe proposed outreach programs for recruiting women, minorities, or disparate populations.
- How you will minimize undue influence in recruitment?
- Attach copies of all recruiting and advertising materials (emails, verbal scripts, flyers, posts, messages, etc.).

For additional information on recruiting and advertising:

- [IRB Application Instructions - Advertisements](#)
- [PI Guide to Identification and Recruitment of Human Subjects for Research](#)

Participants will be recruited based on the following inclusion criteria: Pregnant women at 6-32 weeks gestational age; History of OUD; Who are receiving MAT and obtaining prenatal care at one of the 12 study sites. Patients will be identified by site research nurse (to be determined), viable pregnancy by ultrasound report will be confirmed and diagnosis of OUD and taking MAT will be confirmed. Patient will then be approached about possible recruitment in study. Each study site will have a contracted study nurse who will be identified, CITI trained and added to the IRB for patient recruitment. Although, not an inclusion or exclusion criteria, we have noted that a substantial proportion of potential study participants are under some type of criminal justice supervision at some point during their study participation. We have added a question to the study screener. Importantly, we will not screen or enroll women who are incarcerated in a detention center, easily identified by clothing worn by inmates and/or under escort or restrained by a guard or handcuffs.

Clinical Referrals - clinical providers in the Division of Maternal Fetal Medicine, Department of OB-GYN, provide telemedicine consultations to women with high risk pregnancies through the Kentucky Angels program. At the end of a patient's regular telemedicine consultation, the provider will briefly describe the PATH Home study to potentially eligible patients using a standard script. If a patient is interested in learning more about the study, the provider will ask the patient if it is okay for the research nurse at the PATH Home study site to contact them. If yes, the provider will ask the patient to provide a telephone number that can be shared with the research nurse. The provider will also explain to the patient that their contact information (name and telephone number) will be shared a member of the research team who will contact the research nurse at the study site. The provider will add a note in "ViewPoint" (the ultrasound reporting system), documenting that the study was discussed with the patient, she was interested in learning more about the study, she gave permission for the research nurse at the study site to contact her, and provided a phone number.

Potential participants will be recruited for this study from among the patients presenting for prenatal care with OUD of pregnancy at any of the aforementioned study sites across the state of KY. Clinic providers and research staff may use a flyer as a recruitment tool with their patients. In addition, clinics may provide the flyer to other community-based providers and organizations and disseminate at community events to promote awareness about the study and referrals.

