## Prisoner Categories

- Category 1: My research involves the study of possible causes, effects, processes of incarceration, and of criminal behavior.** (Processes of incarceration can be interpreted broadly to include substance abuse research, half-way houses, counseling techniques, criminal behavior, etc.)
- Category 2: My research involves the study of prisons as institutional structures, or of prisoners as incarcerated persons.** (This category is usually used fairly narrowly – i.e., looking at prisoner diet, conditions of prison, etc.)
- Category 3: My research involves the study of conditions particularly affecting prisoners as a class.** (This category is rarely used – e.g., vaccine trials, research on hepatitis, social and psychological problems such as alcoholism, drug addiction, sexual assaults. Minimal risk studies should not go under this category.)
- Category 4: My research involves the study of practices, both innovative and accepted, which have the intent and reasonable probability of improving the health or well-being of the subject.** (Rare for research involving placebo or control groups to fall in this category because of the difficulty in justifying improvement of the health or well-being of the subject being given placebo or in a control group.) Note: Contact the Office of Research Integrity at [contact] for more information.
- Epidemiologic Research Involving Prisoners [See also SECTION 3 below]**

Explain the research practices that will be used in this study and how they are intended to improve the health and well-being of the participants:

All enrolled study patients will receive a standardized prenatal education curriculum for OUD in pregnancy. Sites have been randomized to receive group prenatal education ("group" arm) imparted through a nurse facilitator and peer support specialist, or through telemedicine sessions with experts in nursing and substance abuse counseling.

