**Attachments****Informed Consent Process:**

Using active voice, describe how investigators will obtain consent/assent. Include:

- the circumstances under which consent will be sought and obtained
- the timing of the consent process (including any waiting period between providing information and obtaining consent)

- who will seek consent
- how you will minimize the possibility of coercion or undue influence
- the method used for documenting consent
- if applicable, who is authorized to provide permission or consent on behalf of the subject
- if applicable, specific instruments or techniques to assess and confirm potential subjects' understanding of the information

Note: all individuals authorized to obtain informed consent should be designated as such in the E-IRB "Study Personnel" section of this application.

Special considerations may include:

- Obtaining consent/assent for special populations such as children, prisoners, or people with impaired decisional capacity
- *Research Involving Emancipated Individuals*  
If you plan to enroll some or all prospective subjects as emancipated, consult with UK legal counsel **prior to submitting this application to the IRB**. Include research legal counsel's recommendations in the "Additional Information" section as a separate document.
- *Research Involving Non-English Speaking Subjects*  
For information on inclusion of non-English speaking subjects, or subjects from a foreign culture, see IRB Application Instructions for Recruiting Non-English Speaking Participants or Participants from a Foreign Culture.
- *Research Repositories*  
If the purpose of this submission is to establish a research repository describe the informed consent process. For guidance regarding consent issues, process approaches, and sample language see the [Sample Repository/Registry/Bank Consent Template](#).

Potential research subjects (those who are identified as being 6 - 32 weeks gestational age, with Opioid Use Disorder on Medication Assisted Therapy), will be approached for study enrollment by the trained study site research nurse. Study site research nurse (TBD) will consent patient for study enrollment. There is no required waiting period between informing prospective subject and obtaining consent. Only English speaking patients will be consented for study enrollment.

Patient participation or non-participation in the research protocol will not impact their routine clinical care in any way (prenatal or substance use care)

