See HIPAA/Consent form (UK Sites) and Consent form (Non-UK Sites). We have updated the study consent forms to note that women under criminal justice supervision will not have information about participation disclosed to probation or parole and their decision to participate will not affect their status with any criminal justice agency, treatment, parole, or other agency. Participant complaints may be fielded by either the primary PI or via the patient's primary obstetric care clinician. At the end of each session, participants will be asked if they have any questions or concerns, and contact information will be disseminated to participants. PI and attending clinicians will maintain and open line of contact in order to discuss any potential participant complaints or questions. Additionally, the informed consent forms provided to participants will contain all contact information necessary for lodging complaints or withdrawing from the study.

Request for Waiver of Informed Consent Process

If you are requesting IRB approval to waive the requirement for the informed consent process, or to alter some or all of the elements of informed consent, complete, Section 1 and Section 2 below.

Note: The IRB does not approve waiver or alteration of the consent process for greater than minimal risk research, except for planned emergency/acute care research as provided under FDA regulations. Contact ORI for regulations that apply to single emergency use waiver or acute care research waiver [contact]).

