**Objectives**

List your research objectives. Please include a summary of intended research objectives in the box below.

Aim 1.) Conduct a randomized cluster trial using a 'hub and spoke' study design, comparing two delivery modes (local GROUP care vs TELEMEDICINE) for the delivery of a PATHways based patient education curriculum at participating regional sites. Each regional site will be randomized to support one of two study arms: 1) Prenatal group care led by a Perinatal Nurse Facilitator and Peer Support Specialist (GROUP arm); or, 2) Telemedicine consultation provided by a Perinatal nurse educator, substance abuse counselor and/or Peer Support Specialists based at the 'hub' site (TELEMEDICINE arm).

Aim 2.) Evaluate the relative effectiveness of each study arm on primary and secondary maternal and neonatal outcomes as compared to the established PATHways program (UK-PATHways: Hub) at the University of Kentucky.

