**Study Design**

Describe and explain the study design (e.g., observational, secondary analysis, single/double blind, parallel, crossover, deception, etc.).

- *Clinical Research:* Indicate whether subjects will be randomized and whether subjects will receive any placebo.
- *Community-Based Participatory Research:* If you are conducting [community-based participatory research \(CBPR\)](#), describe strategies for involvement of community members in the design and implementation of the study, and dissemination of results from the study.
- *Qualitative research:* Indicate ranges where flexibility is needed, if a fixed interview transcript is not available, describe interview topics including the most sensitive potential questions.
- *Research Repositories:* If the purpose of this submission is to establish a Research Repository (bank, registry) and the material you plan to collect is already available from a commercial supplier, clinical lab, or established IRB approved research repository, provide scientific justification for establishing an additional repository collecting duplicate material. Describe the repository design and operating procedures. For relevant information to include, see the [UK Research Biospecimen Bank Guidance](#) or the [UK Research Registry Guidance](#).

We will perform a stratified cluster randomized controlled trial with randomization of participating clusters into a "GROUP CARE" or "TELEMEDICINE" arm. Sites will be stratified into "high volume" (>500 deliveries/year) and "low volume" (<500 deliveries/year). Randomization will be 1:1 within each strata. According to 2016 site specific delivery data, 6 sites are "low volume" and 6 sites are "high volume". All enrolled study patients will continue to receive regular prenatal care (PNC) through their community based obstetric

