Telemedicine arm consultations will be provided by study personnel identified within this application including [name], [name] and [name].

**GROUP CARE ARM:** Study participants at the clusters randomized to the "group" arm will receive group care at 2 week intervals initiated from study enrollment. Group care sessions will be led by an on-site perinatal nurse facilitator and a local peer support specialist. The prenatal group sessions will be imparted in a structured fashion with each session lasting for 45-60 minutes. The content matter discussed will follow a rotating curriculum comprising 8 core sessions over a 16 week period, and will be repeated at each study site as long as there are enrolled active study patients. Once a patient is 8 weeks postpartum ,she will be seen monthly until 6 months postpartum. Data will be collected at each visit by trained study site personnel and entered in a secured online database (REDCap).

**TELEMEDICINE ARM:** Study participants at the clusters randomized to the telemedicine arm will receive the intervention through a telemedicine platform as part of the Kentucky Angels telemedicine program. The division of maternal fetal medicine has established a platform for obstetric outreach addressing perinatal issues pertaining to high risk pregnancies across Kentucky. As part of this cluster RCT, participants at study sites randomized to this arm will receive these telemedicine-based consultations with providers from perinatal nurse educators, peer support specialists, and substance abuse counselors at the University of Kentucky every two weeks until 8 weeks postpartum - and then monthly until 6 months post-partum. Should the patient have the need for additional sessions with a specialist, these will be provided . Data will be collected at each visit by trained study site personnel, and entered into a secured online database (REDCap). See data management plan for more information on the data storage.

The supplemental clinical care that patients will consist of a standardized rotating 8 topic patient education curriculum, including the following topics: 1. Treatment Options for Opioid Use Disorder 2. Smoking Cessation 3. Relapse Prevention Education 4. NAS Reduction Education 5. Breast Feeding Support/Education 6. Domestic Violence Education 7. Postpartum Depression 8. Birth Control/Family Planning.

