14. Anxiety: GAD7 administered at intake, 3rd trimester, 3 and 6 months postpartum
15. Quality of life: WHO QoL-BRF administered in 3rd trimester, 3 and 6 months post-partum
16. Mother-Infant dyad status/Foster care requirement: retention of custody evaluated by patient interview at hospital discharge, 3 and 6 months postpartum
17. Maternal breastfeeding status: evaluated by patient interview at delivery, 3 and 6 months postpartum.

We will be collecting the following fetal data:

Fetal size per gestational age; Any genetic or structural anomalies; any other fetal complications.

We will be collecting the following neonatal data, including the following assessments:

Gestational age and weight at birth; 5 & 10min Apgar score; NICU/nursery hospital admission; NAS diagnosis & treatment requirement (primary outcome); NAS medication days; in-hospital growth (birth to discharge per day); other infant morbidities; total hospitalization length of stay; immunization compliance, ED visits, follow up with scheduled pediatric visits.

Data will be obtained via medical record review, patient interview, physician/staff report, review of state Medicaid data, and hospital discharge data by the study site research staff with the oversight of the UK-study team.

We will perform fidelity monitoring of intervention delivery. Research nurses/facilitators (group arm), providers (telemedicine arm), and all study participants will be asked to complete a fidelity form, similar to an evaluation form, at the end of each educational session. We will evaluate intervention fidelity by comparing provider and participant responses. If any discordance is identified between provider and participant responses for a given topic, additional training related to intervention delivery may be required.

In each arm, patients will be randomly selected to participant in a qualitative interview process at each participating site at the time of the 6 month postpartum follow-up. The interviews will be facilitated by Co-I [name], who has extensive experience using qualitative techniques with substance-involved patients in community based and treatment settings, with the assistance of research coordinators trained in qualitative interviewing techniques. Patients will be offered a fifty dollar stipend for their time to participate in the interview. 3 patients will be randomly selected from each participating site for a total of 33 interviews.

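### Women are recruited by the site nurse after the site's arm is fixed, with no described masking and no record by arm of who was approached or declined, so arm-dependent consent could bias the NAS comparison unseen.

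*Combined protocol and SAP*

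**What the plan says.** - **Allocation.** Under Objectives, "Each regional site will be randomized to support one of two study arms". Study Design adds "Randomization will be 1:1 within each strata", with six high-volume and six low-volume sites. The Prisoner Categories section reports this as done: "Sites have been randomized to receive group prenatal education".
- **Start of the arm-specific intervention.** Under Research Procedures, women at GROUP sites "will receive group care at 2 week intervals initiated from study enrollment".
- **Recruitment.** In Subject Recruitment Methods & Advertising, the site research nurse identifies women and confirms a viable pregnancy, opioid use disorder (OUD) and medication treatment; "Patient will then be approached about possible recruitment in study".
- **Consent.** Under Informed Consent Process, candidates "will be approached for study enrollment by the trained study site research nurse", who also obtains consent.
- **Analysis.** The SAP calls for noninferiority on the primary outcome, which the protocol identifies as NAS. It uses a mixed model in which covariate adjustment is optional.

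**The concern.** Randomising sites balances sites on average. It does not balance the women who agree to join once each site's mode of delivery is settled. The two offers look different to a woman deciding whether to take part: meeting locally with other women who have OUD, or speaking to staff remotely. The Background section itself names stigma and travel as obstacles for rural patients, and either could affect uptake of one mode more than the other. A recruiter who knows the mode may also, without intending it, approach different women.

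If the women who enrol differ by arm in their risk of NAS, the contrast mixes the effect of delivery mode with the effect of selection. In a noninferiority comparison this can hide a real disadvantage or create an apparent one. Enrolling more women does not remove it. Without counts of women approached and declining, neither the sponsor nor a reader could judge whether it happened.

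**Working it through.** **1. Order of events.** The plan gives no date for site randomisation relative to the first enrolment. The order follows from two statements: the sites are described as already randomised, and arm-specific sessions begin from enrolment. A site's arm is set once, so under rolling recruitment essentially every woman is approached at a site whose mode is already fixed.

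**2. Who knows the arm.** That the recruiter is unmasked is an inference. It is close to certain, because Study Design has facilitators sought at sites that drew GROUP and site staff collect data at each visit. No section describes masking, an independent recruiter, or identification of women before randomisation.

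**3. What existing provisions cover.**

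| Provision | What it leaves open |
|---|---|
| Screener and confirmed eligibility (Subject Recruitment) | No stated record of decliners, and no report by arm |
| Standard script (Subject Recruitment, Kentucky Angels referrals) | One route only; the site nurse still makes contact and takes consent |
| Information to eligible women (Prisoners, Condition 3) | No record of who was approached or refused |
| Planned against achieved recruitment, twice a year (Data and Safety Monitoring) | Not said to be by arm; no eligible or declined counts |
| Intake instruments (Schedule of Study Assessments) | Describe enrolled women only; order relative to the first session not stated |
| Covariate adjustment (SAP) | Optional, and cannot reach unmeasured differences |

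**4. Illustration of size.** The plan has no figure to reproduce: it gives no NAS rate, margin, alpha, intracluster correlation (ICC) or consent rate. Every input here is assumed except the maximum of 267 women and the 12 sites.

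Assume half of eligible women are higher-risk, all consent rates are 70% except among higher-risk women in one arm (rate c), and there is no true arm effect.

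- Higher-risk share in the affected arm: s = 0.5c / (0.5c + 0.5 × 0.70). In the other arm it is 0.50.
- Spurious difference = (0.50 − s) × (NAS risk in higher-risk women − NAS risk in the others).
- For c = 0.50: s = 0.25/0.60 = 0.417. For c = 0.30: s = 0.15/0.50 = 0.300.

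To see what this does to a noninferiority claim, suppose the affected arm is the one being tested and is truly worse by exactly the margin. The nominal 2.5% chance of wrongly declaring noninferiority becomes Φ(b/SE − 1.96), where b is the spurious difference. The margin cancels. SE uses 133 women per arm (267/2) and design effect 1 + (267/12 − 1) × ICC, which is 1 at ICC 0 and 1 + 21.25 × 0.05 = 2.06 at ICC 0.05. As an approximation, the variance is taken at the no-effect rates.

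| NAS risks | c | Spurious difference | False noninferiority, ICC 0 | ICC 0.05 |
|---|---|---|---|---|
| 60% and 40% | 50% | 0.083 × 0.20 = 1.7 points | 4.6% | 3.8% |
| 60% and 40% | 30% | 0.200 × 0.20 = 4.0 points | 9.6% | 6.6% |
| 70% and 30% | 50% | 0.083 × 0.40 = 3.3 points | 7.8% | 5.7% |
| 70% and 30% | 30% | 0.200 × 0.40 = 8.0 points | 25.9% | 14.8% |

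Worked example, row 2: the overall rates are 50% and 46%, so SE = √[(0.25 + 0.2484)/133] = 0.0612, b/SE = 0.04/0.0612 = 0.653, and Φ(−1.307) = 9.6%. If the selective refusal occurs in the reference arm, the bias reverses and noninferiority becomes harder to show.

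**The case against.** Recruitment after randomisation is hard to avoid in a cluster trial that enrols women as they present at 6 to 32 weeks. Both arms are active, with the same eight topics, frequency and payments, so there is less reason for uptake to diverge than against usual care. That stands, although the mode of delivery still differs.

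The magnitude is also assumed. Without clustering, the standard error of a difference near 50% is √(2 × 0.25/133) = 6.1 points, so the milder scenarios fall well inside sampling error. The 8-point case needs a 40-point drop in consent in one arm together with a 40-point risk gap, and nothing in the documents suggests either. This stands too, but bias does not shrink with sample size as sampling error does.

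Three stronger readings are tempting and are not supported:

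- **That there is no safeguard.** Several partial ones exist, as tabulated above. None is aimed at consent differing by arm.
- **That the GROUP recruiter is also the facilitator.** This rests on one phrase about fidelity forms: "Research nurses/facilitators (group arm), providers (telemedicine arm), and all study participants will be asked to complete a fidelity form". The recruitment section describes a contracted study nurse at each site, and the facilitator is described separately. Research Procedures has facilitators trained at all 11 sites, while Study Design confines them to GROUP sites. Overlap is possible but not established.
- **That recruitment materials differ by arm.** The flyer and consent texts are not in the supplied documents. Consent forms are distinguished by type of site ("See HIPAA/Consent form (UK Sites) and Consent form (Non-UK Sites"), and one flyer is named, so the wording may already be neutral.

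**Conclusion.** The point holds as a gap in detection and mitigation. The plan fixes the site's arm before women are approached, gives identification and consent to the site nurse, describes no masking, and requires no record by arm of eligible, approached, consenting and declining women. Consent that depends on delivery mode could therefore bias the noninferiority comparison of NAS in either direction without being noticed. The existing provisions reduce the risk only in part.

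A reader might infer that the trial is biased by some number of points. The documents do not support that: size and direction are unknown, and the figures of about 2 to 8 points illustrate assumed consent rates and NAS risks. The conclusion rests on two inferences, that site nurses know their site's arm and that sites were allocated before recruitment began. The sponsor should act on this, since the remedy is inexpensive.

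**What to change.** 1. **Recruitment and intake.** Extend the existing referral script to all recruitment by site nurses. Confirm that the flyer and consent text are the same in both arms. Complete every intake instrument before any arm-specific contact.
2. **Log.** Have the existing site nurse keep a consecutive, de-identified log: eligible, approached, consented, reason declined, gestational age and medication agent. Obtain IRB agreement on what may be kept about women who decline. Report the log by site and arm, with baseline characteristics by arm.
3. **Analysis.** In place of optional adjustment, prespecify a sensitivity analysis of NAS adjusted for intake measures already collected (addiction severity, smoking, depression, anxiety) and for gestational age at entry and medication agent. State that it cannot correct unmeasured selection, for example on fear of exposure.

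Concealing a site's mode until after consent is not requested. It would withhold known information about what a woman will receive, and because participants are paid for referrals that enrol, referred women may already know the mode.

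The cost is a little more site paperwork and one extra analysis. Randomisation and intervention are unchanged. Recruitment that has already taken place can be covered only from whatever screener records exist.
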